3.4 Other analyses (secondary endpoints in pivotal study)

This endpoint is defined as:

- Proportion of patients with positive-margins after standard of care breast-conserving surgery who have a LUM Imaging System signal in the cavity above the threshold as defined by the tumor detection algorithm (i.e., a positive LUM signal). The endpoint is estimated as:

$$\frac{\# \text{ positive margin patients after SOC with LUM signal above the threshold}}{\# \text{ positive margin patients after SOC}}$$

- Proportion of subjects with pathology-positive margins after standard of care breast-conserving surgery, for whom additional therapeutic shaves resulted in pathology-negative margins. Note: This efficacy metric also estimates the potential reduction in re-excision surgeries following standard of care breast-conserving surgery that resulted from a positive SOC margin. This is estimated as:

$$\frac{\# \text{ positive margin patients after SOC with all final negative margins after the LUM procedure}}{\# \text{ positive margin patients after SOC}}$$

- Mean absolute volume (cc) of tissue removed from therapeutic shaves. For each subject, absolute shave volume will be calculated as length (c) \times width (c) \times depth (c) for each therapeutic shave with the sum by subject of all therapeutic shaves. Dimensions for the tissue will be obtained as entered in the case report form from the standard of care pathology report. Subjects with no therapeutic shaves taken will have a therapeutic shave volume of 0cc. The proportion of the subjects with and without therapeutic shaves will be reported. The mean and median (with 90% confidence interval) of the total surgery volume of tissue excised and total volume of the SOC tissue will be reported grouped by the subjects with or without therapeutic shaves.

LUMICELL CONFIDENTIAL

This document is confidential. Do not disclose or use except as authorized.

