- c. Mean contribution of therapeutic shave volume to total volume of tissue removed. The ratio of therapeutic shave volume to total volume of resection (main specimen + SOC shave volume + therapeutic shave volume) tissue removed will be calculated in the total population and in the population with therapeutic shaves removed. For each subject, the volume for each piece of tissue will be calculated as length (c) × width (c) × depth (c), and the dimensions will be obtained as entered in the case report form from the standard of care pathology report. The mean and median (with 90% confidence interval) will be reported.
- d. Average number of SOC shaves and therapeutic shaves taken per subject overall and by type of SOC lumpectomy procedure (i.e., lumpectomy with comprehensive shaves vs. lumpectomy with or without selective shaves).
- e. Number of second surgeries recommended as a result of final positive margins.
- f. Rate of second surgery procedures as a result of final positive margins.
- g. Rate of second surgery procedures as a result of final positive margins.
- h. Rate of cancer found in second surgeries.
- i. Number of second surgeries for each subject.
- j. Number of images per subject from the cavity after SOC and first round of the therapeutic shaves.
- k. Number of LUM images having LUM-positive signal and therapeutic shaves taken.
- l. Fluorescence intensity mean of the cavity images, LUM positive images and positive images with shave after SOC and after one round of the therapeutic shaves.
- m. Number of device issues and malfunctions and their impact to data capture.

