4.4 Methods for additional analyses

Secondary outcomes involving proportions will be analyzed using methods for Binomial distributions akin to the ones described above. Continuous measurement will be summarized using means and standard deviation. The percent of people with a specific AE will be reported in prespecified groups. The percent of subjects with adverse events in subjects that have at least one therapeutic shave will be compared with the percent of subjects with adverse events that have no therapeutic shaves using Fisher's exact test.

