- e. In the case of a therapeutic shave taken but no image saved before the shave was removed, the shave will be excluded from analysis.
- f. In the case of the subject with minor deviation, like no blood drawn, high blood pressure, etc., data will be kept for device performance evaluation.
- g. In the case of SOC shave is taken after use of the Luminicell imaging system, if there is an image for this shave, it will be kept for sensitivity and specificity analysis. If there is a therapeutic shave ahead of the SOC shave but the orientation of the SOC shave is not the same as that of the therapeutic shave taken before it, this SOC shave will be kept for the margin analysis. If the orientation of the SOC shave is same as that of the therapeutic shave taken before it, this SOC shave should be removed from the margin analysis. If there is no therapeutic shave ahead of the SOC shave, this deviated SOC shave will be kept as SOC shave for margin analysis.
- h. In the case of a patient having bilateral lumpectomy, only the data collected from the trial side will be included in the device performance evaluation.
- i. In the case of multiple reports margins and tumors for one block of shave, the distance of the closest margin will be used and ‘Yes’ for the shave containing tumor if at least one report for that block is ‘Yes’.
- j. In the case of the unknown dimension of the shaves or 999 for any of the dimensions, the volume of the shave is the average of that of all the existing shaves of the corresponding type (SOC or Therapeutic).
- k. In the case of a tissue has unknown or unreported distances to margins, the data in the eCRF will indicate “unknown”, it will be interpreted as no specified distance has been reported or the options in the eCRF do not fit the distance description in the pathology report and/or the pathology worksheet. However, the determination for positive or negative margins in the corresponding orientations will depend the pathology determination on whether margins are positive or negative. For example, a pathology report may state “closest margin to invasive cancer is 1mm in medial”. Thus it is assumed that the margins for the other orientations are > 1mm but the specific distance is not reported. For orientations other than medial, the eCRF may indicate “unknown” for margin distance, but the margin status will be considered as “negative” for data analysis.

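### SAP 4.8.3 item j replaces a whole shave volume by the type mean when one dimension is unknown, so recorded dimensions are discarded and the descriptive volume summaries lose accuracy

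*SAP*

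**What the plan says.** - SAP 3.4 defines volume as length × width × depth. One listed metric is "Mean absolute volume (cc) of tissue removed from therapeutic shaves", summed per subject, with 0 cc for a subject without therapeutic shaves. Item c adds "The ratio of therapeutic shave volume to total volume of resection (main specimen + SOC shave volume + therapeutic shave volume"), and there "For each subject, the volume for each piece of tissue will be calculated as length" × width × depth, so the main specimen needs all three dimensions as well.
- On the source, item c says that "the dimensions will be obtained as entered in the case report form from the standard of care pathology report".
- On precision, item c says "The mean and median (with 90% confidence interval) will be reported". The preceding volume item writes the same 90% interval for total surgery volume and SOC volume. SAP 4.4 adds: "Continuous measurement will be summarized using means and standard deviation".
- The missing-data rule is SAP 4.8.3 item j. Its trigger is "In the case of the unknown dimension of the shaves or 999 for any of the dimensions". Its consequence is that "the volume of the shave is the average of that of all the existing shaves of the corresponding type (SOC or Therapeutic"). The average is within shave type. The text does not say whether it is taken across the study or within subject; across the study is the natural reading.
- Item j names shaves only. No rule is stated for an unknown dimension of the main specimen.

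**The concern.** One missing dimension is enough to trigger item j, and the sentence leaves no room for using the other two. Yet length and width say a good deal about volume: a large shave with no recorded depth is still known to be large. Giving it the volume of an average shave ignores that. Three consequences follow:

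- the individual volume is estimated less accurately;
- a block of identical central values pulls in the spread;
- if larger shaves are the ones that lack a dimension, the mean is pulled down.

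These volumes describe how much extra tissue the device causes to be removed. SAP 3.4 labels the group as secondary endpoints in the pivotal study, so the same rule could be carried forward.

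**Working it through.** The SAP gives no figure for this rule, so there is none to reproduce. It also gives no shave sizes, variability, correlation or missingness rate. These are assumed.

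**Assumptions.** Set A: lognormal dimensions with means 3.5 × 2.5 × 0.8 cm, CVs 35%, 35% and 40%, depth missing. Set B: medians 3.0 × 2.0 × 0.8 cm, CVs 35%, 35% and 50%, one dimension missing at random. Correlation between log dimensions is 0 to 0.6; m = 5%, 10% or 20% of shaves affected.

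**1. Error per imputed shave (set A, missing at random).**
- Independent dimensions: mean volume = 3.5 × 2.5 × 0.8 = 7.0 cc, and CV² = 1.1225 × 1.1225 × 1.16 − 1 = 0.4616.
- Item j: RMSE = SD of volume = 7.0 × √0.4616 = 4.76 cc.
- Keeping length and width and filling depth: root-mean-square area × depth SD = (8.75 × √1.26) × 0.32 = 3.14 cc. The ratio is 4.76/3.14 = 1.5.
- Correlation 0.6, depth predicted by log-scale regression: log variances are 0.1156, 0.1156 and 0.1484. The log variance of volume is 0.3795 + 0.4530 = 0.8325, so CV² = e^0.8325 − 1 = 1.299. With R² = 2(0.6²)/1.6 = 0.45, the residual log variance is 0.1484 × 0.55 = 0.0816. The ratio is √{1.299 / [2.299 × (1 − e^−0.0816)]} = 2.7.
- Simulation of set B: 4.50/2.81 cc = 1.6 at correlation 0 and 10.06/3.59 cc = 2.8 at correlation 0.6 (20% missing). When missingness rises with area, set A at correlation 0.6 reaches about 2.9.

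**2. Spread.**
- Shave level, missing at random: the SD is multiplied by √(1 − m), a change of −2.5%, −5.1% and −10.6% at m = 5%, 10% and 20%. A standard error that treats imputed values as observed is (1 − m) times the complete-case one.
- Per-subject sums: if the number of shaves is Poisson (mean 2, say; the mean cancels), the SD is multiplied by √{1 − m·CV²/(1 + CV²)}. At m = 10%, set A with independent dimensions gives √(1 − 0.1 × 0.4616/1.4616) = 0.984, or −1.6%. At correlation 0.6 it is √(1 − 0.1 × 1.299/2.299) = 0.971, or −2.9%. So about 2%.

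**3. Mean.**
- Missing at random: no material bias under item j (within 0.2% in simulation).
- Missing depth with probability proportional to shave area, set A, independent dimensions: the imputed value equals the observed mean, so the bias is −CV²(area) × m/(1 − m), with CV²(area) = 1.1225² − 1 = 0.26. This gives −1.4%, −2.9% and −6.5% at 5%, 10% and 20%. At correlation 0.6 and 10% missing, simulation gives −7.7%.
- Set B, with the larger half of shaves missing three times as often: −2.8% to −3.8% at 10% missing.

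**4. The remedy under the same conditions.** Predicting the missing dimension from the recorded ones has about 0% bias when missingness is random or depends on recorded area. When it depends on the volume itself, the bias at 10% missing is −0.2% to −0.9%. The shave-level SD still falls by about 0.8% to 1.9% at 10% missing at random, against about 5% under item j.

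**The case against.** The strongest reply is that little depends on this. SAP 1 says the protocol had no pre-defined, hypothesis-tested endpoints, and SAP 3.4 lists the volumes under other analyses. Residual-cancer removal, sensitivity, specificity and margin status do not use volume, and SAP 4.8 plans subject-level listings. All of that stands.

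Three stronger readings are tempting and are not supported:

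- **That item j biases the mean as such.** It does so only if missingness is related to size. The documents give neither a rate nor a pattern.
- **That the planned 90% intervals are materially too narrow.** The direction is right, but the √(1 − m) factor applies to single shaves. For per-subject sums the effect is about 2% of the SD at 10% missing. For total volume it is below 0.2% even at 20% missing, if the main specimen is assumed to average 90 cc with a CV of 66%. No 90% interval is written for mean therapeutic volume itself.
- **That a 999 for a main specimen would be multiplied in as a length.** No text says so, the code appears only for shaves, and item j shows that the authors treat 999 as missing. What the text does show is that a missing main-specimen dimension has no stated rule.

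A further fair objection concerns the simplest repair, filling the missing dimension with its own mean. With correlated dimensions this is biased even when missing at random (about −0.7% to −1.5% at 10% missing, where item j is unbiased). It reaches about −4.8% with area-related missingness at correlation 0.6. That argues for predicting the dimension, not for keeping item j.

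**Conclusion.** The point holds as a small analysis-choice issue. Item j discards recorded measurements, and a better rule is available from data already in the case report form. The loss of accuracy per imputed shave (about 1.5 to 2.9 times the RMSE) and the shrinkage of spread hold throughout the assumed range. The downward bias in the mean, about −3% to −8% at 10% missing, is conditional on larger shaves lacking a dimension more often. Every magnitude depends on assumed sizes, correlations and missingness. If few shaves have an unknown dimension, the practical effect is negligible. Nothing beyond the descriptive volume metrics in SAP 3.4 changes.

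**What to change.** Reword SAP 4.8.3 item j as follows:

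1. Keep every recorded dimension. Predict only the missing one, by regression on the log scale from the recorded dimensions among complete shaves of the same type, with a back-transformation correction (such as a smearing factor). Then multiply.
2. Use the mean volume of the shave type only when no dimension is recorded, and say that this mean is taken across the study.
3. Apply the same approach to the main specimen, using complete main specimens, and state that 999 is a missing code wherever it appears.
4. Report the number of imputed pieces by type, and repeat the volume summaries on complete cases.

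The cost is a few sentences in the SAP, a little more programming and slightly wider intervals. No new data are needed.

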3.1 Definition of positive margins

For this study, positive margins were defined using the latest consensus from the Society of Surgical Oncology as follows:

- For invasive cancer with or without associated carcinoma in situ: cancer cells present on ink [1]
- For pure DCIS lesions: DCIS present within 2 mm from the inked surface [2]. Note: when microinvasive cancer is reported, the positive margin criterion will be the same as for pure DCIS instead of the criterion for invasive cancer per NCCN Clinical Practice Guidelines in Oncology.

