- l. For reported microinvasive cancer, adjudicated correction will be provided external to the eCRF and will be used to change the margin type from Invasive to DCIS following NCCN guidelines.
- m. Margins for SOC and final margins will be derived from the tumor distance to margins. If there is a discrepancy between the derived margins based on distance and the margin status determined by the clinical site (could be due to different criteria used by the clinical sites), adjudication of the margin status will be done by Luminicell based protocol defined margin criteria (section 3.1).

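### SAP 4.8.3(k) sets margin status for unknown distances without regard to tumour type, so under the 2 mm rule for pure DCIS and microinvasive cancer a negative call is not secured

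*SAP*

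**What the plan says.** SAP 3.1 sets two criteria. Invasive cancer, with or without in situ disease, is positive only when tumour is on ink. The other criterion is "For pure DCIS lesions: DCIS present within 2 mm from the inked surface". When microinvasive cancer is reported, "the positive margin criterion will be the same as for pure DCIS instead of the criterion for invasive cancer".

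Three items in SAP 4.8.3 then govern how status is obtained:

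- **Item k** covers any tissue whose margin distance is unknown or unreported. Status "will depend the pathology determination on whether margins are positive or negative". An example follows: the report gives 1 mm as the closest distance to invasive cancer, in the medial orientation. "Thus it is assumed that the margins for the other orientations are > 1mm but the specific distance is not reported", and the other orientations are analysed as negative.
- **Item l** retypes microinvasive margins from invasive to DCIS by a correction held outside the eCRF. It does not mention unknown distances.
- **Item m** gives the general rule: "Margins for SOC and final margins will be derived from the tumor distance to margins". If the derived status differs from the site's, the sponsor adjudicates under section 3.1. Item m names sites' use of other criteria as one possible cause of such a difference.

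Margin status is the third-level truth standard in SAP 3.3.2, used for an imaged orientation with neither a shave nor a re-excision. It also defines the positive-margin denominator and the final-negative count in SAP 3.4.

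**The concern.** Item k has no tumour-type limit, but section 3.1 has two thresholds. Patients with pure DCIS are eligible (protocol 6.1.1). Margins are assessed by each institution's own practice (protocol 5.4.3) at up to 20 sites. A pure DCIS or microinvasive report that gives only a closest distance, or none, is therefore foreseeable.

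For such a report, neither of item k's supports establishes a negative margin under section 3.1. The site's determination may rest on another criterion, and lying farther away than a 1 mm closest margin does not put an orientation beyond 2 mm.

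At stake are the truth standard for sensitivity, specificity and the Youden Index and, less often, the margin endpoints. The SAP bases these analyses on the pivotal study's proposed endpoints, and protocol 15.5 uses the combined Phase B and C data to power that trial.

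**Working it through.** **1. Does the example's inference hold?** Apply section 3.1 to a margin known only to be more than 1 mm away. I read a distance of exactly 2 mm as within 2 mm.

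| True distance | Invasive (positive on ink only) | Pure DCIS or microinvasive (positive within 2 mm) |
|---|---|---|
| 1.1 mm | negative | positive |
| 1.5 mm | negative | positive |
| 2.0 mm | negative | positive |
| 2.5 mm | negative | negative |
| 5 mm | negative | negative |

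The example is valid for invasive cancer at every distance. Under the 2 mm rule, exceeding 1 mm does not settle the status.

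**2. When is the status open under the 2 mm rule?** Let d be the closest distance reported.

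- d beyond 2 mm: every other orientation is also beyond 2 mm, so negative is correct.
- d within 2 mm: the named orientation is positive. The others may be positive or negative.
- No distance given: status rests on the site's determination alone, under whatever criterion the site used.

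**3. Do items l and m close the gap?** Take a microinvasive case reported as in item k's example. Under the ink rule all orientations are negative. Item l then retypes the margins to DCIS. For the medial orientation at 1 mm, item m derives positive, finds a discrepancy with a negative site status, and sends it to adjudication. The other orientations have no distance, so nothing is derived, no discrepancy arises and the negative status stands unchecked. The same holds for a pure DCIS orientation that a site calls negative without a distance.

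**4. Which way does an error go?** Suppose the margin is the truth standard and a positive orientation is recorded as negative.

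- LUM-negative: a false negative is counted as a true negative. Sensitivity and specificity both rise, which favours the device.
- LUM-positive with no shave or re-excision (the surgeon declined, or the shave limit was reached; SAP 4.8.3): a true positive is counted as a false positive. Both fall, which counts against the device.

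**5. How large could it be?** The SAP states no figure to reproduce, and the documents do not say how many pure DCIS or microinvasive orientations lack a distance. For illustration only, take 51 positives (the 19 + 32 of protocol 15.2) and assume 48 detected, so reported sensitivity is 48/51 = 94.1%.

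| Hidden positives, m | All LUM-negative: 48/(51 + m) |
|---|---|
| 1 | 48/52 = 92.3% |
| 2 | 48/53 = 90.6% |
| 3 | 48/54 = 88.9% |
| 5 | 48/56 = 85.7% |

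If the one hidden positive were LUM-positive instead, the true value would be 49/52 = 94.2%, barely different from the reported 94.1%. On these counts, sensitivity is more exposed to LUM-negative errors.

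**The case against.** **The distance sentence is an example, not the rule.** A reader might infer that item k declares every margin with unknown distance negative because it is more than 1 mm away. The text does not say that. The rule is the pathology determination, and the example concerns invasive cancer, where it is correct. This stands. What remains is that the rule has no tumour-type limit and relies on a determination that item m allows may follow other criteria.

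**Hidden positive margins are not shown.** This also stands. The documents establish that such margins could pass unchecked, not that any did.

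**Not every error favours the device.** Correct, as step 4 shows.

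**The patient-level effect is narrower than it looks.** If a pure DCIS report names a 1 mm margin, that margin is already positive, so the patient is in the SAP 3.4 denominator whatever happens to the other orientations. A false final-negative result needs a further condition, such as the named orientation being converted by a therapeutic shave while another lies at 1 to 2 mm. This stands.

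**Source pathology may hold the answer.** Item k counts a distance as unknown even when the report's description simply did not fit the eCRF options, and item l's correction is adjudicated outside the eCRF. Usable information may therefore exist. But no item requires anyone to look for it, so the handling remains unspecified.

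**The illustration mixes units.** The 51 counts Phase B and C imaged surfaces for the algorithm lock, not tissues under the Phase C truth standard. The table should not be set against the protocol's margin of error of about 7% as if the two measured the same thing.

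**Conclusion.** The gap is real and limited. Following items k, l and m as written can give a pure DCIS or microinvasive orientation a negative status that conflicts with section 3.1, with no step that would detect it. The microinvasive route needs nothing beyond the SAP's own wording.

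The effect cannot be sized from the documents. The sensitivity figures above rest on an assumed 48 of 51 and an assumed number of hidden positives. They show only that one LUM-negative error would move an estimate of this size by about 1.8 points (94.1% to 92.3%). The direction of the net effect depends on the mix of LUM-negative and LUM-positive orientations, which is also not given.

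This is a should-fix. SAP section 1 states that the protocol predefined no hypothesis-tested endpoints, so no formal conclusion turns on it, but the estimates feed the powering of the pivotal trial.

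**What to change.** Amend SAP 4.8.3 as follows:

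- State that the example in item k applies to invasive cancer only.
- For pure DCIS, and for microinvasive cases after item l, accept negative with an unknown distance only if the report's closest distance is beyond 2 mm, or the report says that the other margins are.
- Otherwise query the site for the existing pathology information and adjudicate under section 3.1.
- If the distance is still unknown, treat the status as missing: neither a truth negative nor a negative final margin. Report sensitivity, specificity, the Youden Index and the SAP 3.4 margin endpoints with these orientations set all positive and then all negative, and give their number by LUM result.

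The cost is a few sentences in the SAP, a few site queries, and a few orientations left without a truth value in the main analysis.

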## 1 PURPOSE

We recently completed Phase A and Phase B of our Feasibility Study of the LUM Imaging System (NCI funding 5R21CA173762-02): Feasibility clinical study of real-time tumor bed imaging in breast cancer patients. Based on the experience gained from this work, we propose to expand the Feasibility Study into multiple institutions (Phase C) with the main goal of standardizing the training for surgeons and clinical staff and to collect additional imaging and pathology data to further refine and verify the tumor detection algorithm. Phase C of the Feasibility Study will be expansion to a maximum of 20 sites, with each site having approximately 1-3 surgeons participating. The study may include up to 250 patients. This study remains non-randomized and open label.

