### 5.3 Main lumpectomy specimen and shaved cavity margins nomenclature

Throughout this protocol, reference is made to the orientation of the main specimen, the SCMs and the lumpectomy cavity walls. When a lumpectomy is performed, there are typically 6 surfaces defined for orienting the main specimen. Typically, final margin assessment is made for each orientation. **Figure 4** shows a schematic representation of the nomenclature for the lumpectomy cavity margins for a right-sided breast lumpectomy, showing 5 orientations. The sixth orientation (not shown in the figure) is the “anterior” margin which is the margin nearest to the skin. For surgeons performing selective or comprehensive SCMs, a shave may not be removed from the

LUMICELL CONFIDENTIAL

This document is confidential. Do not disclose or use except as authorized.

anterior orientation if the lumpectomy cavity extends to the skin or subcutaneous fat. Similarly, a SCM from the posterior orientation (also referred to as “deep”) may not be removed if the lumpectomy cavity reaches the fascia over the pectoralis major or serratus anterior muscle. Shaved cavity margins removed under the guidance of the LUM Imaging System will be named “therapeutic shaves” to distinguish them from standard of care SCM. Please see Appendix C for the guidelines on naming the resected tissue.

**Figure 4:** Schematic representation of the surfaces of the lumpectomy cavity walls (white circle). The posterior margin is nearest the fascia of the pectoral muscle. The anterior margin (not shown) is nearest the skin.

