## 13 DATA AND SAFETY MONITORING

### 13.1 Data reporting

#### 13.1.1 Method

Lumicell will collect, manage, and monitor data for this study.

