3.3.2 Definition of truth standard for diagnostic performance

The instrument diagnostic accuracy is measured by sensitivity and specificity on a per-tissue basis. Because a LUM-guided shave does not exist when a negative LUM image is indicated we propose a hierarchical approach to determine the truth standard as depicted in Figure 2. The highest truth standard is whether pathology finds cancer in a tissue shave removed from the area that was imaged in the cavity. When a shave does not exist, then whether tumor is found in a re-excision surgery is considered as the truth standard. When neither a shave nor a second surgery exists for a given orientation that was imaged, the margin assessment of that orientation is used as truth standard. We believe that the hierarchical approach outlined to determine the truth standard is the most meaningful and practical assessment of device accuracy to predict the presence of cancer in the cavity.

LUMICELL CONFIDENTIAL

This document is confidential. Do not disclose or use except as authorized.

True positive = truth standard positive & Lum cavity image positive

False negative = truth standard positive & Lum cavity image negative

True negative = truth standard negative & Lum cavity image negative

False positive = truth standard negative & Lum cavity image positive

Figure 2: Definition of truth standard to evaluate the LUM Imaging System diagnostic performance.

When a therapeutic shave and re-excision are not available for an orientation, the margin from the prior resected tissue of the corresponding orientation will be used as ground inferred truth for evaluation (Figure 3).

The orientation of the tissue removed during a re-excision is typically noted in the pathology report and matches the orientation in which a positive margin was identified from the initial surgery. However, there will be instances in which the orientation of the tissue removed during a re-excision is not specified. In cases of unclear orientation of the tissue removed during re-excisions, it will be assumed that the re-excision was intended to address only the orientations with positive margins and pathology findings from the re-excision (tumor found/not found) will be applied to those orientations.

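### The sponsor settles disputed margin status, which can be the truth standard for the device, and the SAP specifies no masking to the LUM result

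*SAP*

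**What the plan says.** SAP 4.8.3 item m derives SOC and final margins from tumour distance. The trigger for adjudication is narrow: "If there is a discrepancy between the derived margins based on distance and the margin status determined by the clinical site". In that case "adjudication of the margin status will be done by Luminicell based protocol defined margin criteria", with SAP 3.1 as the reference. Item l adds an adjudicated correction of margin type for microinvasive disease, held outside the eCRF.

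SAP 3.3.2 sets a hierarchy for truth: pathology of a shave from the imaged area, then re-excision findings, and failing both, "the margin assessment of that orientation is used as truth standard". It notes that "a LUM-guided shave does not exist when a negative LUM image is indicated", so the top level is normally missing at LUM-negative orientations. The cell at issue is defined as "False negative = truth standard positive & Lum cavity image negative".

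On the setting, Protocol 1 states "This study remains non-randomized and open label" and Protocol 13.1.1 states "Lumicell will collect, manage, and monitor data for this study". The independent bodies in Protocol 13.2 and 13.4 review safety only. Neither document describes masking of margin adjudication, an independent efficacy reader, or an analysis on the site's own margin status.

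**The concern.** A diagnostic accuracy estimate is credible when the truth label is set without knowledge of the test result. Here the party that owns the device and manages the data also settles disputed truth labels, and the plan is silent on whether the LUM result is hidden at that moment. At a LUM-negative orientation whose truth rests on the margin, a negative call gives a true negative and a positive call a false negative.

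The same calls reach further:
- They set both denominators, and the conversion numerator, of the positive-margin proportions in SAP 3.4.
- They decide whether a LUM-positive orientation left unshaved counts as a detection when there was no re-excision (SAP 4.8.3).
- Where re-excised tissue has no stated orientation, they decide which orientations receive its pathology finding (SAP 3.3.2).

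No efficacy hypothesis is tested in Phase C. However, its results support the algorithm lock (Protocol 15.2) and, pooled with Phase B, the powering of the pivotal trial (Protocol 15.5). Biased labels would carry forward.

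**Working it through.** **Step 1: which orientations are directly exposed.** Reading SAP 3.3.2 and 4.8.3 together, an orientation's false-negative or true-negative status turns on this adjudication only if all of these hold: it was imaged and LUM-negative; no shave was taken there; no re-excision covers it; and distance-derived and site status conflict. Although "there are typically 6 surfaces defined for orienting the main specimen" (Protocol 5.3), most orientations will have undisputed margins. The documents do not count the disputed ones.

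**Step 2: how much judgement is left.**
- Several reports on one block: the closest distance is used (item i).
- Unknown distance: pathology's positive or negative determination is followed (item k).
- Thresholds: tumour on ink for invasive disease; within 2 mm for pure DCIS and for microinvasion (SAP 3.1).
- Lesion type stays open. Tumour at 1 mm is negative under the invasive criterion and positive under the DCIS criterion, so classifying the lesion sets the truth. The microinvasive rule is in SAP 3.1 but not in Protocol 5.2.1, so the criteria are not wholly those of the protocol.
- Item m itself expects conflicts because sites may apply different criteria.

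**Step 3: the plan's own sizing figure (Protocol 15.2).** Phase B gave 19 pathology positives in 40 patients: 19/40 = 0.475 per patient. A further 32 need 32/0.475 = 67.4 patients, against about 67 stated, so the figure reproduces. The total is 19 + 32 = 51. The target is a margin of error of about 7% in sensitivity; neither the confidence level nor the assumed sensitivity is given. At 95%, 1.96 × √(0.93 × 0.07/51) = 0.070, so an assumed sensitivity near 0.93 would match.

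**Step 4: effect of one call (illustration).** Assume 51 truth positives and a starting sensitivity of about 0.7, 0.8 or 0.9. Moving k false negatives to true negatives gives TP/(51 − k); moving k true negatives to false negatives gives TP/(51 + k).

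| Assumed start | One FN becomes TN | One TN becomes FN |
|---|---|---|
| 36/51 = 70.6% | 36/50 = 72.0% (+1.4) | 36/52 = 69.2% (−1.4) |
| 41/51 = 80.4% | 41/50 = 82.0% (+1.6) | 41/52 = 78.8% (−1.5) |
| 46/51 = 90.2% | 46/50 = 92.0% (+1.8) | 46/52 = 88.5% (−1.7) |

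About four to five calls in the same direction would move sensitivity by the whole 7-point target: 36/46 = 78.3% (+7.7), 41/47 = 87.2% (+6.8), 46/47 = 97.9% (+7.7).

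**Step 5: specificity.** Assume 67 × 6 − 32 = 370 truth-negative orientations and specificity 0.7. Five reclassifications give 264/375 − 259/370 = 0.704 − 0.700, or 0.4 points. At higher specificity the change is smaller. The Youden Index would therefore move almost one for one with sensitivity.

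**The case against.** The strongest reply is that item m is a consistency check and not a judgement call. It applies one written distance rule where sites used different ones, and multiple and unknown distances already have rules. A margin that the site calls positive usually leads to second surgery in that orientation, and re-excision pathology then outranks the margin. Phase B reported no false negatives in the cavity walls (Protocol 3.2 and 5.1), and with none there is nothing to reclassify as a true negative. This is also a feasibility study without efficacy hypotheses.

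Much of this stands. It narrows the exposed set to that in step 1 and confines discretion mainly to lesion type and the resolution of conflicts. It does not remove the gap: a site-negative, distance-positive margin with no re-excision is exactly the case in which the adjudicated call is the truth. The Phase B result also does not protect Phase C, which adds sites and surgeons.

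A reader might go further and infer that adjudicators work with the LUM result in view. The documents do not say so; they are silent. A reader might also infer that most LUM-negative truth labels are in the sponsor's hands. Margin status may well be the truth for most such orientations, but only disputed margins reach item m.

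**Conclusion.** The point holds as a gap in the plan: the sponsor adjudicates discrepant margin status, that status can be the truth standard and feeds the margin endpoints, and no masking to the LUM result is specified. It is worth correcting, because the guard is cheap and these accuracy estimates inform the pivotal trial.

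The actual size is unknown, since the number of disputed margins is not given. The 1.4 to 1.8 points per reclassified false negative rest on assumed sensitivities of 0.7 to 0.9 and an assumed 51 truth positives. That 51 pools Phase B with Phase C and counts imaged surfaces containing cancer, which are not the same as margin-positive orientations.

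A reader might infer that sensitivity will be inflated. The documents do not support a direction: uniform criteria can turn a site-negative margin positive, and item l moves cases to the wider 2 mm criterion, which at a LUM-negative orientation counts against the device.

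**What to change.** Amend SAP 4.8.3 items l and m as follows.

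- **SOC margins:** the same sponsor staff adjudicate from a listing without LUM results or any therapeutic-shave data.
- **Final margins:** these may lie on a therapeutic shave (Protocol 5.4.3), so shave pathology cannot simply be withheld. The listing shows only tumour distance and lesion type, with the LUM result and the tissue label (SOC or therapeutic) removed.
- **Order of work:** lock margin status before it is merged with imaging data.
- **Reporting:** list every changed call, and repeat sensitivity, specificity and the SAP 3.4 margin endpoints with the site's unadjudicated status.

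The cost is a masked listing and one repeat table. No further patients or adjudicators are needed. Masking may be incomplete for staff who already know a case, which is why the repeat analysis is needed as well. If adjudication is already masked in practice, stating so in items l and m closes the masking part of the point.
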